4.1. Clinical Investigation Procedures and Follow-up Schedule

The Clinical Investigation visits will occur as in-clinic visits at Baseline, Procedure, Discharge, 14 and 30-days follow-up.

The Flow Chart and the Follow-up phases of this clinical investigation are described in Figure 4-1 below.

[figure not shown]

Figure 4-1. Flowchart of the clinical investigation schedule

The scheduling of the clinical investigation visits will include the following:

Baseline visit (Visit 1)

During the baseline visit, the patient will be informed about the clinical study and provide signed informed consent form if surgeon decides that the patient is eligible as applicable. [REDACTED]
[REDACTED]
[REDACTED]
[REDACTED]

[REDACTED] In case of pregnancy, the patient will withdraw of the study a [REDACTED]
[REDACTED].

Procedure – (Visit 2)

The study population consists of subjects that provided signed ICF, met all inclusion criteria and none of the exclusion criteria, and successfully undergo surgery with the Bitrack System and its corresponding ESE/NESE instruments. These patients will be followed up until 30 days post-procedure. On the other hand, those subjects

in whom robot assisted laparoscopic radical/simple nephrectomy is attempted but not achieved will be followed-up for 30 days, but not included as population for analysis.

For research purposes, we will consider the start of the procedure at the moment of docking, meaning the moment when the camera of the robot is introduced inside the trocar. Therefore, all procedures that started but do not proceed with the use of the Bitrack system or are converted into a conventional laparoscopic/open surgery are included under the Intent-to-treat (ITT) population. Any robot assisted surgery converted to conventional laparoscopic/open surgery due to reasons different than the failure of the Bitrack System and its corresponding sterile endoscopic surgical instruments will be excluded from the endpoint analysis. █

This event will be considered a procedure failure.

CONFIDENTIAL
PI-PR01-027 A2

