5. ENDPOINTS

5.1. Primary Endpoint

The primary safety and performance endpoints of this early feasibility investigation are:

1. Evaluation of the safety of the Bitrack System by measuring the occurrence of Procedure-Related Adverse Events (PRAEs) and Serious Adverse Events (SAEs) during the procedure and through the 30 days post-procedure period of enrolled patients indicated for robot assisted laparoscopic radical/simple nephrectomy.
2. Evaluation of the performance of the investigational devices by means of its ability to access and reach the target zone, perform all relevant surgical tasks and to be withdrawn efficiently without conversion to MIS or open surgery. The performance of the Bitrack System and the ESE/NESE instruments will be analyzed through the conversion rate to conventional laparoscopy/open surgery.

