9.2. Statistical Analyses

9.2.1. Primary Safety and Feasibility Endpoint Analyses

The primary safety and performance endpoints of this early feasibility investigation are:

- 1) Evaluation of the safety of the Bitrack System by measuring the occurrence of Procedure-Related Adverse Events (PRAEs) and Serious Adverse Events (SAEs) during the procedure and through the 14-days and 30-days post-procedure period of enrolled patients indicated for robot assisted laparoscopic Radical/simple nephrectomy surgery.

- 2) Evaluation of the performance of the investigational devices by means of its ability to access and reach the target zone, perform all relevant surgical tasks and to be withdrawn efficiently without conversion to MIS or open surgery.

Considering the low number of subjects, no formal hypothesis has been defined for this clinical investigation.

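### Section 4.1 drops conversions not due to device failure from the endpoint analysis, although the primary performance endpoint is the conversion rate with no limit on cause

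*Protocol*

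**What the plan says.** Section 5.1 of the Protocol states the second primary endpoint in terms of what the devices can do, and says that their performance "will be analyzed through the conversion rate to conventional laparoscopy/open surgery". Section 9.2.1 repeats the idea of success: the devices should reach the target zone, "perform all relevant surgical tasks and to be withdrawn efficiently without conversion to MIS or open surgery". The summary at the front of the Protocol words it as 5.1 does. None of these places limits the cause of a conversion.

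Section 4.1, under the procedure visit, sets the start of the procedure at docking. It then says that started procedures which do not go on with the robot "or are converted into a conventional laparoscopic/open surgery are included under the Intent-to-treat (ITT) population". The next sentence provides that surgeries converted for reasons other than "the failure of the Bitrack System and its corresponding sterile endoscopic surgical instruments will be excluded from the endpoint analysis". A blacked-out stretch follows, and then a short sentence that classes some event as a procedure failure; which event is meant cannot be seen.

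Three other provisions bear on the same subjects:

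- An earlier paragraph of 4.1 keeps subjects whose robotic nephrectomy was tried but not completed under 30-day follow-up, yet outside the population for analysis.
- Section 6.4 counts a patient as enrolled only once treatment with the device has succeeded.
- Section 9.1.1 defines the ITT population as those in whom treatment with the device was tried and not completed.

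**The concern.** The endpoint as defined counts every conversion. The rule in 4.1 takes out one class of them, and because it takes out the whole surgery, the subject leaves the denominator as well as the numerator. Whether a conversion belongs to that class is a judgement on cause, which can be made only once the conversion has happened. Section 7.3 makes the study open-label, and the visible text names neither criteria nor an independent assessor for the judgement.

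No type I error is at stake, since 9.2.1 sets no formal hypothesis. What is at stake is the descriptive conversion rate, which is the measure that 5.1 names for performance. Section 9.3 says that the study is meant to find the limitations and advantages of the system and to inform the freezing of its design. A conversion left out of the rate is information of just that kind.

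**Working it through.** The Protocol derives no sample size, power or alpha, so there is no planned figure to reproduce. The check is the effect of the rule on the rate.

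**Inputs.** Sample size 3 (6.1.1). Endpoint: conversion, no cause stated (5.1, 9.2.1). Exclusion: conversions not due to failure of the system or its instruments (4.1).

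**Formula.** Let n be the procedures started, c the conversions and x the conversions judged non-device.

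- All-cause rate: c/n.
- Rate under the exclusion: (c − x)/(n − x).
- Difference: c/n − (c − x)/(n − x) = x(n − c)/[n(n − x)].

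The difference is never negative. It is positive whenever x > 0 and c < n. It is zero if x = 0, or if every case converts and only some are excluded. If all are excluded, the rate is 0/0.

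**All cases with x > 0 for n = 3, no replacement** (exact Clopper-Pearson 95% limits in brackets):

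| c | x | All-cause | After exclusion |
|---|---|---|---|
| 1 | 1 | 1/3 = 33.3% (0.8 to 90.6%) | 0/2 = 0% (0 to 84.2%) |
| 2 | 1 | 2/3 = 66.7% (9.4 to 99.2%) | 1/2 = 50% (1.3 to 98.7%) |
| 2 | 2 | 2/3 = 66.7% (9.4 to 99.2%) | 0/1 = 0% (0 to 97.5%) |
| 3 | 1 | 3/3 = 100% (29.2 to 100%) | 2/2 = 100% (15.8 to 100%) |
| 3 | 2 | 3/3 = 100% (29.2 to 100%) | 1/1 = 100% (2.5 to 100%) |
| 3 | 3 | 3/3 = 100% (29.2 to 100%) | 0/0, undefined |

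**If excluded cases are replaced.** The same formula applies, with n as the total started. Take four started, one non-device conversion and no other conversion: all-cause 1/4 = 25%, reported 0/3 = 0% (0 to 70.8%). The direction is unchanged.

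**How often the rule would bite.** The documents give no conversion probability, so these are assumptions. For a per-case probability p of a non-device conversion, the chance that at least one of 3 cases is affected is 1 − (1 − p)³:

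- p = 5%: 1 − 0.95³ = 14.3%
- p = 10%: 1 − 0.90³ = 27.1%
- p = 20%: 1 − 0.80³ = 48.8%

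**What the rate then estimates.** With assumed device and non-device probabilities d and p, the all-cause rate is d + p and the rate after exclusion is d/(1 − p):

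- 5% and 5%: 10% becomes 0.05/0.95 = 5.3%
- 10% and 10%: 20% becomes 0.10/0.90 = 11.1%
- 5% and 15%: 20% becomes 0.05/0.85 = 5.9%
- 10% and 20%: 30% becomes 0.10/0.80 = 12.5%

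**The neighbouring clauses.** A conversion caused by the device is also a robotic nephrectomy that was tried and not completed. The earlier paragraph of 4.1 would therefore put it outside the analysis population, and 6.4 would leave the subject unenrolled. Taken literally, no converted case remains and the rate is 0 by construction. That cannot be squared with an endpoint that counts conversions, nor with the 4.1 sentence that places converted procedures in the ITT.

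**The case against.** The strongest reply is that 5.1 concerns the performance of the devices, so 4.1 may simply be its operational rule: count the conversions that the device caused. Such a rate is a legitimate measure, and the all-cause reading of 5.1 rests on its silence about cause. This stands in part. But neither 5.1 nor 9.2.1 defines the endpoint that way, and a device-attributed rate does not require removing the other subjects from the denominator.

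The redaction after the exclusion sentence is a real limit. Attribution criteria, an assessor or a replacement rule may lie behind it. If the event called a procedure failure is the non-device conversion, the text would count that case as a failure and also exclude it, which adds a contradiction and removes none. Even perfect attribution would leave the mismatch with 5.1.

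The broad definition of device deficiency in 8.1.3, which includes misuse and use error, might keep more conversions in the count if it governs the word failure in 4.1. The text does not say that it does.

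The study is exploratory, section 4 calls statistical analysis not applicable, no visible decision threshold depends on the rate, and the intervals for 1/3 and 0/2 overlap almost wholly. All of this is true, and it confines the harm to descriptive reporting.

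A reader might infer more than the documents support:

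- *That the rule always favours the device.* It can never count against it, but it changes nothing when all 3 convert and only some are excluded.
- *That the denominator must shrink.* Because 6.4 counts only successful treatments towards the 3 subjects, an excluded case might be replaced.
- *That harms in converted subjects will be lost.* This follows only if the endpoint analysis in 4.1 is taken to include safety. Follow-up to 30 days is kept in 4.1, all adverse events are assessed under 5.2, and 4.2.2 requires full source verification of them.
- *That ITT membership and the exclusion are logically incompatible.* A subject can belong to a population and still be left out of one analysis. The firm contradiction is between the exclusion and the endpoint.

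**Conclusion.** The concern holds. The primary performance endpoint is stated without a limit on cause, and 4.1 removes from its analysis a class of conversions identified after the outcome in an open-label study. The rule can leave the rate unchanged, lower it or make it undefined; it cannot raise it. One non-device conversion among 3 moves the result from 33% to 0%, assuming that the excluded case is not replaced; with replacement the size differs but the direction does not. The probabilities of 14% to 49% that the rule comes into play rest on assumed conversion rates of 5% to 20% and serve only as illustration. That attribution is uncontrolled is not established, since the relevant text may be redacted. Loss of safety data is possible but not shown. The neighbouring clauses in 4.1, 6.4 and 9.1.1 belong to the same defect, because removing the one sentence would leave them in force.

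**What to change.** - **4.1:** delete the exclusion of conversions not due to device failure, and delete the clause that keeps uncompleted robotic cases out of the analysis population.
- **6.4 and 9.1.1:** define enrolment and the ITT population to cover every eligible, consented subject whose Bitrack procedure was started, with docking as the start as 4.1 already has it, whether the procedure was completed or converted.
- **Primary conversion rate:** all conversions of any cause, divided by all started procedures.
- **Reporting:** list the cause of each conversion, and give the device-attributed rate as a secondary line on the same denominator.
- **Safety:** keep all started subjects in the 30-day safety endpoint.

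The cost is a few sentences in 4.1, 6.4 and 9.1.1, and a conversion rate that may look less favourable. No new patients or data are needed, since 30-day follow-up of these subjects is already required.

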4.2. Measures Taken to Avoid and Minimize Bias

The following steps will be taken to minimize bias in the conduct of the clinical study:

4.2.1. Subject requirement

Patients of both genders will be considered as anatomy does not influence the surgical approach.

A [REDACTED]

4.2.2. Safety monitoring

Measures taken to avoid bias related to safety includes 100% of source data verification related to AEs documented in the Monitoring Plan.

4.2.3. [REDACTED]

[REDACTED]

[REDACTED]

CONFIDENTIAL
PL-PR01-027_A2

5. ENDPOINTS

5.1. Primary Endpoint

The primary safety and performance endpoints of this early feasibility investigation are:

1. Evaluation of the safety of the Bitrack System by measuring the occurrence of Procedure-Related Adverse Events (PRAEs) and Serious Adverse Events (SAEs) during the procedure and through the 30 days post-procedure period of enrolled patients indicated for robot assisted laparoscopic radical/simple nephrectomy.
2. Evaluation of the performance of the investigational devices by means of its ability to access and reach the target zone, perform all relevant surgical tasks and to be withdrawn efficiently without conversion to MIS or open surgery. The performance of the Bitrack System and the ESE/NESE instruments will be analyzed through the conversion rate to conventional laparoscopy/open surgery.

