Clinical Investigation Design	This is a single-center, early feasibility, and first in human (FIH) clinical investigation with a single arm, open label and non-randomized design
Primary Endpoints	
The primary safety and performance endpoints of this early feasibility investigation are:
 
 1) Evaluation of the safety of the Bitrack System by measuring the occurrence of Procedure-Related Adverse Events (PRAEs) and Serious Adverse Events (SAEs) during the procedure and through the 30 days post-procedure period of enrolled patients indicated for robot assisted laparoscopic radical/simple nephrectomy. 2) Evaluation of the performance of the investigational devices by means of its ability to access and reach the target zone, perform all relevant surgical tasks and to be withdrawn efficiently without conversion to MIS or open surgery. The performance of the Bitrack System and the ESE/NESE instruments will be analyzed through the conversion rate to conventional laparoscopy/open surgery.

 CONFIDENTIAL
 PL-PR01-027_A2

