5.2. Secondary Endpoints

The secondary endpoints planned for this clinical investigation are listed below:

- All AE(s) events during the procedure and through the 14- and 30-days post-procedure will also be assessed, and therefore relationship with the investigational device and/or procedure will be examined by the principal investigator and reported to Rob Surgical
 - Timeframe: Procedure, discharge, 14- and 30 -days follow up visits
- Individual safety (i.e., absence of unwanted injure of any tissue) and performance (VAS scale 0-10 following the subjective surgeon's opinion, being 0 a non-functional tool and 10 an instrument that works exactly equivalent to the surgeon's hands) for each instrument surgical function.
 - Timeframe: Procedure
- Blood Loss defined as estimated mL of blood loss, transfusion rates and use of haemostasis agents
 - Timeframe: Procedure
- Operative Time Procedure measurement for the different tasks.
 - Timeframe: Procedure
- To evaluate post-operative pain in patients through the Cumulative Analgesic Consumption Score (CACS) during the first week (7days) post-procedure.
 - Timeframe: Discharge
- To assess the duration of subject's hospitalization as the Length of Stay (LoS) in hospital calculated from day of admission to day of discharge.
 - Timeframe: Discharge
- Patient pain assessment via VAS. Patient interview questions
 - Timeframe: Discharge, 14- and 30-days post-procedure
- Post-procedure complication rates, including the measurement of the comprehensive complication index (CCI) on a scale from 0 (no complications) to 100 (death), and the Clavien-Dindo classification, which consists of 7 grades (I, II, IIIa, IIIb, IVa, IVb and V), the first one indicating any deviation from the normal postoperative course, the highest-grade indicating death
 - Timeframe: Discharge, 14 and 30 days follow-up

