8.2. Device Relationship

Determination of whether there is a reasonable possibility that an investigational product or device under investigation caused or contributed to an AE is to be determined by the **Investigator** and recorded on the appropriate CRF form. Determination should be based on assessment of temporal relationships, evidence of alternative etiology, medical/biologic plausibility, and patient condition (pre-existing condition).

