8.3.2. Determination of Adverse Events related to device and/or procedure

As detailed in Section 5.1, the primary endpoint of the study is to measure the safety and performance of Bitrack System. Among the ratios to be measured, the rate of death occurrence (SAE) during the surgery related directly to the use of the Bitrack System and the rate of any adverse event (AE) occurrence during the surgery directly related with the procedure and/or device under investigation will be determined.

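### The primary safety measure is defined inconsistently: the synopsis, 5.1 and 9.2.1 name no device-related category, while 8.3.2 includes device-related events but only during surgery

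*Protocol*

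**What the plan says.** The primary safety measure appears in four places in the protocol.

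- **Section 5.1** opens with "Evaluation of the safety of the Bitrack System by measuring the occurrence of" two kinds of event. The measure is "measuring the occurrence of Procedure-Related Adverse Events (PRAEs) and Serious Adverse Events (SAEs"), from the procedure to 30 days after it.
- **The synopsis** has the same two components: "measuring the occurrence of Procedure-Related Adverse Events (PRAEs) and Serious Adverse Events (SAEs) during the procedure", again to day 30.
- **Section 9.2.1** repeats the two components and words the window as "during the procedure and through the 14-days and 30-days post-procedure period of enrolled patients".
- **Section 8.3.2** refers back to 5.1 and says what will be measured under the primary endpoint. It lists the rate of death during surgery directly due to use of the device, and "the rate of any adverse event (AE) occurrence during the surgery directly related with the procedure and/or device under investigation will be determined".

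Three other places bear on how events are attributed.

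- **Section 5.2** makes all AEs through day 30 a secondary endpoint, for which "relationship with the investigational device and/or procedure will be examined by the principal investigator".
- **Section 8.2** gives the investigator this task, to be recorded on the CRF: "Determination of whether there is a reasonable possibility that an investigational product or device under investigation caused or contributed to an AE".
- **Section 4.1** has the 30-day visit collect events attributed to the device, to the procedure, or to both. The notes to the AE definition in 8.1.1 likewise list device-related and procedure-related events separately.

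The abbreviation list spells out PRAE. The visible text does not say whether the term includes events caused by the device.

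**The concern.** The objective in section 3 is the safety and performance of the device, and section 9.3 says the results will help to freeze its design. A reader will take the primary safety count as the answer to the device question. Under 5.1, however, a non-serious event can enter that count only if it is labelled procedure-related. Since the protocol elsewhere keeps device and procedure as separate attributions, an event labelled device only is not clearly in, while a non-serious event due to the nephrectomy alone is in.

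Section 8.3.2 then gives a different account, wider on attribution and narrower on time. Two people working from different sections could produce different primary counts from the same three patients. The attribution is made by an investigator who knows the treatment (the study is open label), so the definition should not make the headline result depend on a choice between two overlapping labels.

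**Working it through.** There is no stated figure to reproduce: the three subjects are fixed without a calculation (9.3) and no hypothesis is defined (9.2.1). The check is to take each kind of event and ask where each section puts it.

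| Event | Synopsis, 5.1, 9.2.1 (primary) | 8.3.2 (primary) | 5.2 (secondary, all AEs) |
|---|---|---|---|
| Non-serious, procedure-related, during surgery | counted | counted | reported |
| Non-serious, procedure-related, after surgery to day 30 | counted | not counted | reported |
| Non-serious, device only, during surgery | not expressly counted | counted | reported |
| Non-serious, device only, after surgery to day 30 | not expressly counted | not counted | reported |
| Serious, related to device or procedure, during surgery | counted | counted | reported |
| Serious, unrelated, during surgery | counted | not counted | reported |
| Serious, any attribution, after surgery to day 30 | counted | not counted | reported |

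Three things follow.

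1. The two accounts agree in only two of the seven rows where an event is counted: non-serious procedure-related events during surgery, and related serious events during surgery.
2. They differ on two dimensions. On attribution, 5.1 names the procedure and 8.3.2 names the procedure and/or the device. On time, 5.1 runs to day 30 and 8.3.2 stops with the surgery.
3. The fourth row is the one kind of event that no version makes expressly primary. This stays true if 8.3.2 is read as adding to 5.1 instead of competing with it, because the union of the two still leaves that row out.

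To show the size, assume the count is the number of subjects with at least one qualifying event out of 3, and that the other two subjects have none. The protocol gives no event frequency, so these are illustrations and not predictions.

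- One subject has a non-serious device-only event during surgery: 0/3 under 5.1 read literally, 1/3 under 8.3.2.
- One subject has a non-serious device-only event after surgery, by day 30: 0/3 under both, 1/3 under a definition that includes device-related events to day 30.
- One subject has a non-serious procedure-related event after surgery, by day 30: 1/3 under 5.1, 0/3 under 8.3.2.

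In each case one event moves the count by 1/3, about 33 percentage points.

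**The case against.** The strongest reply is that the device is used only within the robotic operation. Section 4.1 even dates the start of the procedure from the introduction of the robot's camera. Harm from the robot is then naturally procedure-related, and the device-only category is nearly empty. Parts of section 8 are blacked out, so a definition of PRAE may exist there, and its absence from the visible text cannot be held against the plan. This has force. It is why the table says not expressly counted instead of excluded. But sections 4.1, 5.2, 8.1.1 and 8.3.2 all keep the two attributions apart, and the reply does nothing about the different time windows.

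A second reply is that 8.3.2 presents its rates as being among those to be measured, so it need not be a complete definition. That is fair, and it softens the conflict. It does not close the gap after surgery.

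A third is that nothing is hidden: every AE is reported with its attribution, AE data are fully source-verified (4.2.2), and no visible threshold separates 0/3 from 1/3. This stands, and it limits the weight of the point.

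Two stronger readings should be resisted. A reader might infer from 5.1 that non-serious device-related events are left out of primary safety altogether. Section 8.3.2 contradicts that for the period of surgery; a superficial burn from an instrument, for example, would be covered there. A reader might also infer that such an event would appear in only one secondary endpoint. Section 5.2 also has tissue injury by instrument function and post-procedure complications, and 8.3.4 requires device deficiencies to be reported.

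**Conclusion.** The inconsistency is real and worth correcting. Three statements of the primary safety measure name no device-related category, although the stated question is the safety of the device. A fourth includes device-related events but confines them to the surgery. A non-serious event attributed to the device alone, arising after surgery and by day 30, is expressly primary under none of them.

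The consequence is limited to what the headline safety count describes. There are three subjects, no hypothesis and no stated decision rule, and the events concerned are still reported as secondary. The documents do not support saying that device harms go unrecorded or that a formal conclusion would change.

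This rests on two assumptions: that PRAE carries its literal meaning, since the visible text does not extend it to device-related events, and that the blacked-out parts of section 8 do not settle the matter. Only the protocol was available; a statistical analysis plan might resolve the point, but the protocol's own sections would still disagree.

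**What to change.** Use one definition in the synopsis and in sections 5.1, 8.3.2 and 9.2.1: all AEs related to the device and/or the procedure, plus all SAEs whatever their attribution, from the procedure through day 30. State that this replaces PRAE, or that PRAE includes device-related events. Tabulate the events as device-related, procedure-related, both, or unrelated (SAEs only), so that effects of the robot and of the nephrectomy can be told apart. The table layout itself can be left to the analysis plan.

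If the sponsor wants the rates during surgery in 8.3.2, including device-related death, keep them as a named subset of the single definition and not as a second account of the primary endpoint.

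The cost is wording in four places. No new data are needed, because attribution to device and procedure is already examined for every AE under 5.2, and device causality is recorded under 8.2. The one drawback is that the primary count may rise slightly.
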